3 LIST OF ABBREVIATIONS

BAI	Beck Anxiety Inventory
BDI	Beck Depression Inventory
CAB	Citizens Advice Bureau
CI	Chief Investigator
CSRI	Client Service Receipt Inventory
EQ-5D-5L	EuroQol-5L
GP	General Practitioner
GSQ	General Satisfaction Questionnaire
LED-S	Short Life Events and Difficulties Schedule
LCRN	Local Clinical Research Network
MANSA	Manchester Short Assessment of Quality of Life questionnaire
OAS	Other as Shamer Scale
PCRN	Primary Care Research Network
PI	Principal Investigator
PPI	Patient and Public Involvement
RA	Research Assistant
RSQ	Response Style Questionnaire
SWEMWBS	Short form of the Warwick Edinburgh Mental Wellbeing Scale
TAU	Treatment as usual

4 STUDY SUMMARY

Title	Debt Counselling for Depression in Primary Care: An Adaptive Randomised Controlled Trial.
Study location	Primary care settings in England and Wales (lead site Liverpool)
Study aim	To determine the clinical and cost effectiveness of the addition of a Primary Care debt counselling advice service to usual care, for patients with depression and debt.
Study design	Adaptive parallel two group multi-centre randomised controlled trial with nested mixed methods process and economic evaluation. An internal pilot phase will be used to check intervention fidelity and need for cluster randomisation.
Planned number of sites	3 (Liverpool/Cheshire, Plymouth, Bridgend).
Study population	
Main inclusion criteria	Age ≥ 18 ; Scoring ≥ 14 on the Beck Depression Inventory; Self-identifying as having worries about debt.
Main exclusion criteria	Actively suicidal or psychotic and/or severely depressed and unresponsive to treatment; experiencing severe problems with addiction to alcohol or illicit drugs; unable or unwilling to give written informed consent to participate in study; currently participating in another research study including follow-up data collection phase; has received CAB debt advice in the past 12 months; do not want support about debt or money worries provided through GP practice.
Planned sample size	195 patients/arm across both feasibility and main trials if single randomisation or 235 patients/arm across both feasibility and main trials if cluster randomisation.
Study intervention	
Control arm	Debt advice leaflets provided by GP and treatment as usual (TAU).
Trial intervention	Debt advice leaflets provided by GP, debt counselling advice from a Citizens Advice Bureau Advisor and TAU.
Summary of Outcome Measures	
Primary	Beck Depression Inventory II
Secondary	Beck Anxiety Inventory (BAI), short form of the Warwick Edinburgh Mental Wellbeing Scale (SWEMWBS), EQ-5D-5L, Manchester Short Assessment of Quality of Life questionnaire (MANSA), adapted version of the Client Service Receipt Inventory (CSRI), Stanford presenteeism scale, general satisfaction questionnaire (GSQ), short Life Events and Difficulties Schedule (LED-S), The Adult Hope Scale, , Response Style Questionnaire - 24 (RSQ-24), Other as Shamer Scale (OAS), alcohol use Audit questionnaire, substance misuse screening tool (DAST).
Study schedule	
Duration of study	45 months
Study timelines	Set-up 3 months. Internal pilot 11 months. Full trial 25 months. Data cleaning, analysis, reporting 6 months. Total duration 45 months.

End of Trial	Completion of last follow-up visit of last participant
--------------	--

5 BACKGROUND AND RATIONALE

Depression is estimated to affect 5-10% of adults at any one time, and is a common presentation in Primary Care. However, research suggests that only around 2.5% of patients are formally recorded by GPs as having active depression or depressive symptoms^{i,ii}. Alongside anxiety and stress it is considered the commonest cause for prolonged work absenteeismⁱⁱⁱ, as well as presenteeism (working below normal capacity when unwell). Mental ill health is estimated to cost the UK economy £40B per year overall^{iv,v}. Around 11% of the population are estimated to be struggling with personal debt, with evidence of increasing episodes of suicide associated with rising debt which is likely to increase with the worsening economic situation^{vi,vii}.

Most episodes of depression are managed in Primary Care, following the NICE recommended four-stepped approachⁱ. This includes a range of low intensity interventions including short-term talking therapies, social prescribing to support lifestyle changes (e.g. for exercise), and antidepressants for more persistent symptoms. A recent HTA trial^{viii} found a marginal benefit of SSRIs (antidepressants) for new cases of mild-moderate depression managed in Primary Care over treatment as usual (TAU), but many questions about the most cost effective ways to manage depression remainⁱ.

Recognising the increasing burden of indebtedness and the link between debt and mental illness in the Foresight Report^{ix}, the UK government provides web-based advice and guides on debt-management[†] highlighting a range of providers^{††}. Topping this list is the Citizen's Advice Bureau (CAB), a charity-based service which is widely available across the UK in over 3,500 locations, providing support to over 2M people per year. Their principal on-line recommended site is provided by government, funded by statutory levy from the financial services industry, backed by a national advertising campaign: the Money Advice Service website at www.moneyadviceservice.org.uk/. However, those with depression, particularly if from socio-economically deprived groups, may be particularly likely to find on-line services insufficient or inaccessible (due to travel costs and/or low mood), so a locally accessible, nationally provided, advice service may be an important alternative. Debt is commoner among poorer populations and around 1:4 among those experiencing mental health problems, who make up 50% of those with debt overall^{x,xi}. The strategic & economic cases for providing debt advice for people experiencing mental health problems have been made in recent influential reports; and the intervention being proposed here falls within the suggested service provision costs and model^{xii,xiii}. This study explores an intervention designed to provide enhanced access to timely support for people with depression and anxiety about indebtedness, and will provide robust information on its cost effectiveness and acceptability.

6 AIMS AND OBJECTIVES

6.1 Main trial

Aim:

To determine the clinical and cost effectiveness of the addition of a Primary Care debt counselling advice service to usual care, for patients with depression and debt.

[†] http://www.direct.gov.uk/en/MoneyTaxAndBenefits/ManagingDebt/PlanYourWayOutOfDebt/DG_10013291

^{††} http://www.direct.gov.uk/en/MoneyTaxAndBenefits/ManagingDebt/PlanYourWayOutOfDebt/DG_187500

Specific objectives:

- (i) To compare depression between intervention and control groups.
- (ii) To compare anxiety, mental wellbeing, debt/financial status, satisfaction, health-related quality of life and societal costs between intervention and control groups.
- (iii) To explore outcomes referred to in (i) and (ii) in terms of the following potential predictors - substance misuse problems, self-esteem, life events & difficulties, hope, optimism, resilience, and attribution style.
- (iv) To determine core outcome domains and measures using the COMET Initiative approach to define a Standard Outcome Measure for mental health trials in deprived and hard to reach groups in primary care, adapted to this specific study.
- (v) To manualise debt assessment and counselling intervention & joint comprehensive assessment (GP/patient/CAB) for use within the intervention.
- (vi) To recruit new and chronic/recurrent cases from a variety of practices and populations to enhance generalisability.
- (vii) To undertake a mixed method process evaluation to assess fidelity of intervention (using Normalisation Process Theory) and explore reasons for outcome differences and relationship between depression, anxiety, debt, stigma, shame & psychosocioeconomic factors triangulating economic, psychological factors analysis and qualitative interview data.
- (viii) To undertake Knowledge Exchange events to inform adoption into care pathways (implementation).
- (ix) To work closely with Service Users in Research/Patient and Public Involvement groups across the study sites to inform trial methodology, intervention development, aspects of analysis and the implementation of preparatory work.
- (x) To recruit a virtual group of commissioners, providers and Health and Wellbeing board members to check willingness to commission intervention and advise on domains and measures.
- (xi) To work with CAB leads, GPs and PPI advisors on developing the intervention and comprehensive assessment, qualitative topic guides and aspects of data analysis.

6.2 Internal pilot trial

The aim of the internal pilot phase is to test the procedures, recruitment processes and operational strategies that are planned for use in the main trial, identifying and resolving any problems and thereby assessing the feasibility of continuing with the main trial. Specific objectives are:-

- 1) to confirm methods for recruitment of practices
- 2) to confirm the ability to recruit patients via the proposed approaches
- 3) to confirm the acceptability of the study interventions
- 4) to confirm acceptability of data collection (outcome measures)
- 5) to assess contamination and confirm the randomisation method for the main trial
- 6) to assess the level of participant attrition
- 7) to check robustness of data collection systems

- 8) to identify and resolve potential difficulties in implementing the shared assessment
- 9) to assess intervention fidelity

7 TRIAL DESIGN

The study is an adaptive parallel two group pragmatic randomised controlled trial with 1:1 allocation to intervention or control with a nested mixed methods process and economic evaluation (Figure 1). Patients who have current depression and are worried about debt will be recruited through general practices in three areas of UK. After screening and consent, participants will be randomised to receive either General Practice treatment as usual (TAU) supplemented by debt management advice leaflets (control group) or General Practice treatment as usual supplemented with debt management advice leaflets and primary care based CAB debt advice including a shared GP/Advisor comprehensive assessment (intervention group). Primary (Beck Depression Inventory) and secondary (health-related quality of life, cost effectiveness, satisfaction, and explanatory factors) outcomes will be assessed in all participants at baseline, 4 and 12 months. In addition, qualitative in-depth interviews will be undertaken, to explore causal models of how debt counselling works.

The study includes an internal pilot phase in which intervention fidelity will be assessed and implementation problems identified and resolved without change to the intervention, so that data collected in this phase can be used in the final analysis. Both individual and cluster randomisation methods will be used in the pilot phase to assign participants to intervention or control arms with the aim of using individual level randomisation in the main trial if the pilot phase shows no strong evidence of contamination.

8 Trial ENDPOINTS

8.1 Main trial

8.1.1 Primary Outcome

The primary outcome measure is the Beck Depression Inventory II. This is a self-report measure commonly used in studies of depression.

8.1.2 Secondary Outcomes

Secondary outcomes are as follows, to be finalised during the internal pilot trial.

1. Psychological wellbeing, as measured by:

- Beck Anxiety Inventory (BAI)
- Short form of Warwick Edinburgh Mental Wellbeing Scale (SWEMWBS)

2. Health-related Quality of Life, as measured by:

- EQ-5D-5L
- Manchester Short Assessment of Quality of Life questionnaire (MANSA)

3. Health and social care utilisation and employment factors, as measured by:

- adapted version of the Client Service Receipt Inventory (CSRI)
- Fit Note self-reports

- Stanford presenteeism scale
- customised instrument to record personal debt issues

4. Service satisfaction, as measured by:

- General Satisfaction Questionnaire (GSQ)

5. Life Events, as measured by:

- short Life Events and Difficulties Schedule (LED-S)

6. Substance Misuse, as measured by:

- Audit questionnaire (alcohol use)
- Substance misuse screening tool (DAST)

7. Explanatory measures

Three psychological constructs will be assessed, each of which have been strongly associated with depression in previous work and which might reasonably be hypothesised to mediate the debt-depression relationship:

- (i) **Hopelessness:** Adult Hope Scale (Snyder's State Hope Scale)
- (ii) **Shame:** The Other as Shamer Scale (OAS)
- (iii) **Rumination:** Response Style Questionnaire - 24 (RSQ-24)

The feasibility and acceptability of these outcome measures will be monitored in the internal pilot trial along with data utility in order to determine whether to maintain or reduce the full set of outcome, modifier and predictor variables in the main trial.

8.2 Pilot phase

[figure not shown]
Specific outcomes to be measured in the pilot phase include:-

- estimated proportion of eligible patients who consent to the trial
- number of participants recruited during the recruitment stage of the pilot compared to target
- projections of the recruitment and short-term attrition rate for the main study with 95% confidence intervals
- assessment of contamination (see below)
- assessment of patient satisfaction with intervention and outcome measures

Assessment of contamination

The level of contamination in the control arm will be assessed by comparing individually randomised controls with cluster randomised control patients during the internal pilot trial. Uptake of any form of debt counselling by participants in control groups will be monitored at their follow-up visit, as this is the key measurable variable. An absolute and relative measure has been agreed to suggest important problems with contamination - 10 or more from among the 30 individually randomised control participants seeking debt advice, providing this is at least twice as common among individually versus cluster randomised controls. This evidence will be triangulated with evidence from qualitative interviews with participants that indicates their choice to do so was influenced by GP recommendation or more debt-focused assessments or consultations.

Figure.1: Overview of study

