11 RANDOMISATION

In the internal pilot trial, relevant GP practice demographic information will be sent to CTU/study statistician by CRN in England, this activity will be supported by ABMU Health Board in Wales. Four practices (matched on their size and deprivation index score) in each of the three trial localities will be randomised to intervention or control arms and cluster (practice) or individual (patient) level allocation such that six practices are randomised to cluster allocation and six practices to individual allocation. To achieve total population research practice sites may be combined using a hub and spoke approach where available. The randomisation sequences and matching will be computer generated undertaken by an independent statistician working with the CTU. The CTU programming team will run checks before and during the trial to verify the integrity of the randomisation system.

Should the internal pilot show contamination to be a problem, for the main trial, the remaining practices will be randomised to intervention or control stratified by size and the deprivation (higher vs lower) of the populations they serve. If contamination is not found to be a problem, participants would be individually randomised to intervention or control.

Additional practices for the main trial will be identified and recruited once a decision has been made at the end of the internal pilot whether randomisation will be individual or cluster.

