12.1 Treatment as usual

Individuals randomised to TAU will receive GP care, a study-specific debt advice leaflet and RCPsych debt advice leaflet. TAU will begin with an initial consultation with a GP linked to the study. This initial GP assessment appointment should take place within a week of the participant being randomised. As with participants randomised to intervention arm, control arm participants will be contacted by a member of the practice staff to arrange an appointment with a named GP. The initial GP appointment will combine an assessment of both anxiety and depression, an assessment of need regarding medication and psychological therapy, and agreement regarding further treatment. This may include a referral to the local IAPT service and may normally include up to twelve further GP contacts. GPs may refer participants to IAPT services and other interventions as

[figure not shown]
they please and may arrange to review participants at ongoing appointments as required. The GP will provide each participant with a study-specific debt advice leaflet at the initial consultation.

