21 STATISTICAL CONSIDERATIONS

21.1 Sample size

We require 135 patients/arm to have 90% power to detect a clinically meaningful difference in the primary outcome of 3.5 BDI units between groups at 5% two-sided alpha (based on standard deviation (SD) of 9)^{xiv, xv}. Given our analysis of covariance analysis approach to data analysis (see below) this sample size is likely to be conservative. To allow for a cluster allocation, we need to inflate the sample size by a design effect of 1.45 (assuming an intracluster correlation coefficient (ICC) of 0.05 and average cluster size of 10)^{xvi}. In the pilot trial, we will recruit and randomise 120 patients to intervention and control arms nested by individual or cluster randomisation. If the pilot trial demonstrates no strong evidence of contamination (see section 8.2), main trial allocation will proceed at an individual level and we will require a total of 195 patients/arm across both pilot and main trials (allowing for 20% attrition and clustering in pilot trial). If pilot demonstrates strong evidence of contamination, full trial allocation will proceed at a practice level and we will require a total of 235 patients/arm across both pilot and main trials (allowing for 20% attrition and clustering in pilot and full trial). Should the level of outcome clustering within and between practices be higher (i.e. an ICC of 0.10) these sample sizes will provide 80% power (at 5% alpha).

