23 STOPPING RULES GOVERNING PROGRESSION TO MAIN TRIAL

At the end of the pilot trial a range of parameters will be assessed to inform decisions about stopping rules or adaptations to the main RCT design. The decision to progress to the main trial and modify the trial design will be made in close liaison with the Trial Steering Committee and in discussion with HTA. The following stopping rules will be used to inform a decision whether or not to progress to the main trial:

1. Failure to recruit to pilot trial

The aim is to recruit 120 patients from twelve GP practices in the pilot trial over a period of six months (i.e. approximately 10 patients per practice - 2 cluster and 2 individual randomisation sites in each of three localities). If recruitment is <50% of target at the end of the pilot trial despite intense efforts, appropriate CRN support and in the absence of any exceptional or unforeseen barriers that can be overcome through design adaptations, we will propose to the HTA that the trial is not feasible and should be stopped.

2. Lack of acceptability

The number of participants attending one, two or three meetings with a CAB advisor (intervention contacts) and the proportion of these from the most vulnerable populations will be monitored. Based upon our acceptability data outlined above, should attendance rates for un-cancelled CAB appointments fall below 60% overall at the end of the pilot trial, with no evidence of significant improvement as the trial settled in, we would recommend that the intervention is unlikely to be considered to be cost-effective by commissioners, particularly if triangulating data from qualitative interviews & CSRI/service satisfaction measures suggest that many potential clients find it irrelevant or unacceptable.

3. Uncertain commissioning environment

The findings from the pilot trial in terms of assessing the potential value of the intervention, its acceptability and other key markers identified by the commissioning stakeholders will be used to reaffirm their current interest in both supporting the ongoing trial and utilising the results in the future.

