We plan to check for evidence of significant contamination when participants are randomised individually rather than through cluster practices. While the numbers of patients involved in the pilot trial will not allow us to detect small differences we believe it will be possible to detect differences that reflect important levels of contamination (which might be considered to threaten trial reliability). To check for this we will monitor how many participants from control groups have taken up any form of debt counselling at their follow-up visit, as this is the key measurable variable. We have agreed an absolute and relative measure for this (see section 8.2). If we find strong evidence of contamination we would recommend that the full trial should switch to a full cluster randomised allocation.

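### Section 24 says important contamination can be detected, but the section 8.2 rule fires only about 41% of the time at its own threshold, so a rule that does not fire is weak evidence that contamination is absent

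*Protocol*

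**What the plan says.** Section 8.2 compares uptake of any form of debt counselling in the two pilot control groups. Contamination is signalled by "10 or more from among the 30 individually randomised control participants seeking debt advice". A second, relative condition must hold as well: "providing this is at least twice as common among individually versus cluster randomised controls". The result is then set beside interview evidence on whether GPs influenced the choice.

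Section 24 (item 3) concedes that small differences will be missed, but states that "we believe it will be possible to detect differences that reflect important levels of contamination". It gives no error rate, interval or assumed background uptake.

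The result feeds the main design. Section 21.1: "If the pilot trial demonstrates no strong evidence of contamination (see section 8.2), main trial allocation will proceed at an individual level", at 195 per arm; otherwise allocation is by practice, at 235 per arm. Section 23 has the design decision made in close liaison with the Trial Steering Committee and in discussion with the funder.

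**The concern.** The rule puts two cut-offs on two small observed counts, and both must be met. Not meeting them is what leads to individual allocation. If the rule often stays silent when contamination is at the level the protocol itself calls important, its silence says little, and section 24 credits the pilot with a property it lacks there.

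The ratio limb adds a dependence on background uptake. A fixed absolute excess among individually randomised controls is a smaller ratio when the background is higher, so the same excess becomes harder to flag. Uptake of advice by controls narrows the contrast between arms. An undetected problem would therefore carry into an individually randomised main trial and make a null result hard to interpret.

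**Working it through.** **Inputs**
- Pilot size: "In the pilot trial, we will recruit and randomise 120 patients to intervention and control arms nested by individual or cluster randomisation" (section 21.1).
- Split: "six practices are randomised to cluster allocation and six practices to individual allocation" (section 11).
- Practice size: "approximately 10 patients per practice - 2 cluster and 2 individual randomisation sites in each of three localities" (section 23).
- Allocation 1:1 (section 7).
- Background uptake in cluster controls: not stated, so it is varied as an assumption.

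**Reproducing the plan's figure.** 120 / 2 methods / 2 arms = 30 controls per method, which agrees with the 30 in section 8.2. The cluster controls come from about three practices.

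**Model.** X ~ Bin(30, p_ind) is the number of individually randomised controls seeking advice; Y ~ Bin(30, p_clu) is the number of cluster controls. They are independent and follow-up is complete. The rule fires when X ≥ 10 and X ≥ 2Y. Probabilities come from exact enumeration over all (X, Y).

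**True doubling**

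| Individual v cluster | X ≥ 10 | X ≥ 2Y | Whole rule |
|---|---|---|---|
| 33.3% v 16.7% (10/30 v 5/30) | 0.57 | 0.55 | 0.41 |
| 40% v 20% | 0.82 | 0.55 | 0.51 |
| 50% v 25% | 0.98 | 0.54 | 0.54 |
| 60% v 30% | 1.00 | 0.54 | 0.54 |
| 80% v 40% | 1.00 | 0.54 | 0.54 |

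**Same 20-point excess, different backgrounds**

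| Individual v cluster | X ≥ 10 | X ≥ 2Y | Whole rule |
|---|---|---|---|
| 30% v 10% | 0.41 | 0.81 | 0.39 |
| 40% v 20% | 0.82 | 0.55 | 0.51 |
| 50% v 30% | 0.98 | 0.34 | 0.34 |
| 60% v 40% | 1.00 | 0.18 | 0.18 |
| 70% v 50% | 1.00 | 0.08 | 0.08 |

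At a 10% background the count of 10 is the limit; from 20% upwards it is mainly the ratio. If more than 15 of 30 cluster controls seek advice, X ≥ 2Y would need X above 30, so the rule cannot fire.

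**Large contamination, low background.** 40% v 10%: 0.80. 45% v 15%: 0.82. 60% v 20%: 0.89.

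**No contamination (false alarm).** Uptake of 20%, 30%, 40% and 50% in both groups: 0.03, 0.05, 0.03 and 0.01.

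**Sensitivity.** The protocol's ICC of 0.05 is for the BDI; applying it to uptake is an assumption. With beta-binomial clusters of 10, the threshold case is 0.39, and the 20-point cases at backgrounds of 20-50% are 0.49, 0.37, 0.23 and 0.12. With 24 followed up per group (20% attrition), the threshold case is 0.21 if the count stays at 10, and 0.41 if it is scaled to 8.

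**What one result on the threshold would show.** For 10/30 v 5/30 the difference is 16.7 points. Its standard error is √[(0.333×0.667 + 0.167×0.833)/30] = 0.110, so the 95% CI is 16.7 ± 1.96×11.0, about −5 to 38 points before any allowance for clustering. The risk ratio is 2.0 (95% CI 0.78 to 5.15).

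**The case against.** **Any cut-off behaves this way.** A rule that compares a point estimate with a cut-off fires about half the time when the truth lies on the cut-off. This stands. An absolute-difference limb (X − Y ≥ 5 in place of the ratio) fires 46-56% of the time at its own boundary, for backgrounds of 17-50%. The near coin-flip is thus no special flaw of the ratio. It does mean that detectability cannot be claimed at the threshold.

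**Section 24 is simply wrong.** A reader might infer this, but the protocol does not support it. The statement is hedged as a belief, excludes small differences, and is borne out for 30-40-point contamination on a 10-20% background.

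**The rule can hardly ever fire.** A reader might infer this too. It fits only a background near 50% with a 20-point excess, and no section gives such a background. Section 10.2 excludes people with CAB debt advice in the past 12 months, and section 11.3 tries to keep each GP to one arm; both suggest restraint. In the other direction, participants are selected for debt worries, any form of counselling counts, and section 12.1 says "Individuals randomised to TAU will receive GP care, a study-specific debt advice leaflet and RCPsych debt advice leaflet". The background is unknown.

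**The rule is not mechanical.** This also stands: interviews and committee and funder discussion come between the count and the decision. The protocol does not say how they would outweigh a rule that did not fire.

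**Main-trial power would collapse.** Any such figure needs uptake in the intervention arm, the background, and an effect proportional to the uptake contrast. The protocol gives none of these, so no figure is claimed here.

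**Conclusion.** The concern holds in a limited form. Section 24's detectability statement has no supporting calculation and is not met at the protocol's own definition of important contamination, where the rule fires about 41% of the time. At a true doubling it fires at most about 54% of the time for backgrounds up to 45%. For a 20-point excess, detection runs from 51% down to 8% as the background rises from 20% to 50%, and is 39% at 10%. The statement holds only for large contamination on a low background (about 80-89%).

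A rule that does not fire is therefore weak evidence of no contamination, yet it is the stated route to individual allocation, subject to the interviews and committee discussion. The figures assume 30 v 30 controls, complete follow-up and independent responses. The background rates are assumptions shown as a range.

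**What to change.** **Section 24.** Limit the detectability statement to large contamination on a low background. State the rule's detection and false-alarm probabilities over a range of backgrounds. Say that not meeting the rule does not show that contamination is absent.

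**Section 8.2.** Add that the absolute difference in uptake between the two control groups, with a 95% confidence interval that allows for practice clustering, goes to the Trial Steering Committee and is weighed with the rule and the interviews before individual allocation is confirmed.

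**Cost.** Wording and one interval; no new patients or data.

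**Option for the sponsor, not a required correction.** Replace the ratio limb with an absolute difference, for example at least 5 of 30 (X − Y ≥ 5). Detection of a 20-point excess becomes about 64-66% at backgrounds of 20-50%. It gains almost nothing at 10% or below (0.40 v 0.39 at 10%; 0.20 under both at 5%). False alarms rise from about 1-5% to about 3-12%, and each unnecessary switch costs 235 − 195 = 40 more patients per arm. Which error matters more is for the sponsor to judge.
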